 - Preterm birth before 30 weeks: rate of delivery before 29+6 weeks
 - Preterm birth before 28 weeks: rate of delivery before 27+6 weeks
 - Birth weight: median weight (g) of the newborns at birth
 - Fetal or neonatal death: rate of intrauterine demise or neonatal death during the first 24 hours
 - Neonatal morbidity: rate of major adverse neonatal outcomes before discharge from the hospital
 - Intraventricular Haemorrhage (IVH): grades III-IV
 - Retinopathy of prematurity
 - Respiratory Distress Syndrome (RDS): grades II-IV,
 - Need for ventilation > 72 h
 - Necrotising enterocolitis
 - Proven or suspected sepsis, antibiotics (>5 days)
 - Need (Duration in days) for neonatal special care (NICU)
 - Harm from intervention
- Mother:
 - Maternal death
 - Significant maternal adverse events (rate):
 - Heavy bleeding: bleeding that requires a medical intervention
 - Cervical tear: cervical rupture due to the pessary placement
 - Uterine rupture: rupture of the uterus due to contractions or surgery
 - Physical or psychological intolerance to pessary: discomfort or pain due to the pessary that makes daily life uncomfortable (number of cases)
 - Rupture of membranes before 32 weeks: rate of–rupture of amniotic membranes before 31+6 weeks

[figure not shown]
- Infection/inflammation
- Hospitalisation for threatened preterm labour before 32 weeks: requirement of hospitalisation due to preterm contractions that need medical treatment to try to stop them before 31+6 weeks (rate)
 - Mean hospital stay duration: number of days of admittance at the hospital
 - Use of tocolytic treatment: Type of tocolytic, days of treatment, dose

4.2. Description of the trial design.

Open Multicentre International Collaborative Randomized Controlled Trial, in parallel groups, based on intention-to-treat analysis comparing the placement of a prophylactic cervical pessary with usual management in twin pregnancies with shortened cervix ≤ 25 percentile

4.3. Flowchart.

4.4. Description of the medical device and the treatment regimen.

The cervical pessary is a vaginal device (silicone ring) that is used to treat pregnant women for preventing spontaneous preterm birth. This device can be easily placed around the uterine cervix without pain (see annex I).

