This database will be supervised and coordinated by PD [name], Bürgerhospital Frankfurt/M. (Webmaster).

4.8. Identification of data to be collected in the case report files (CRF) that should be considered as data source.

Data will be collected in E-CRF, provided by >[name] Wissenschaft, Berlin< on study software "Castor".

4.9. Definition of what is considered to be the end of the study.

The study will be finished after the 3 year-follow up examination concerning neurodevelopmental disabilities, which will be conducted on the surviving children of the participating patients.

5. Selection and withdrawal of subjects

5.1. Inclusion criteria.

- Dichorionic diamnionic twin pregnancy with
- 16-28 weeks of gestation
- Minimal age of 18 years
- Informed consent signature

5.2. Exclusion criteria.

- Monochorionic twin pregnancy
- Major fetal abnormalities (requiring surgery or leading to infant death or severe handicap)
- Cerclage prior to randomisation
- Uterine malformation
- Placenta previa totalis
- Active vaginal bleeding at the moment of randomization
- Spontaneous rupture of membranes at the time of randomization
- Silicone allergy

- Current participation in other RCT
- Painful regular uterine contractions

5.3. Withdrawal criteria.

If a participant may voluntarily withdraw from treatment or if it is necessary to remove the pessary due to the conditions described before, the patients will be followed as usual until delivery (intention-to-treat analysis).

The death of one twin is not an exclusion criterion for the pessary placement.

The replacement of patients is not applicable in this trial.

5.4. Rescue treatment criteria.

If the cervical length decreases later on during the pregnancy, the management of the pregnancy in each centre will be the usual.

In case of secondary cervical shortening in the follow-up period pessary treatment may be offered as a rescue treatment up to 32+0 weeks of gestation.

Cervical cerclage or progesterone are generally not indicated in twin pregnancies.

6. Treatment of Subjects

6.1. Treatments to be administered.

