A descriptive analysis by preterm birth will be carried out calculating means and medians for quantitative variables and proportions with 95% confidence intervals for categorical variables. In general, statistical comparisons with the pessary arm and the control arms or other group comparisons for primary and secondary outcomes will be performed with stratified tests as well as comparisons in the gestation subgroups. Events will be analysed for each twin and for single children assuming appropriate random effect regression models. Further subgroup analyses regarding the cervical length will be performed (e.g. CL 15 to 25mm and below 15mm). All tests, see also examples in the synopsis, will be two-sided using a significance level of $\alpha=0.05$.

For the primary endpoint we expect to have a drop out rate of up to 25% due to the long follow-up time (3 years) of the study; but we do not expect to have lost data for the secondary endpoints because for these parameters the study has a short follow-up time till time to birth only.

An interim analysis shall be conducted on key safety parameters after birth of 300 twins: the following safety endpoints will be assessed by a one-sided test with $\alpha=1\%$

- on level of the neonates: rate of preterm birth, time to birth, birth weight, death, neonatal morbidity, harm of intervention
- and on the maternal level: rate of hospitalisation for threatened preterm labour < 32 weeks, rate of PRoM <32 weeks, rate of infection / inflammation, rate of physical or psychological intolerance to pessary, rate of SAR/SAE, death.

The trial will be terminated as negative if a disadvantage for the pessary-treatment can be found in one of these tests. To guarantee a high safety level the significance level is chosen more conservatively than in a Bonferroni correction.

All analysis will be carried out with SPSS® version 19.0 or later (IBM Company SPSS Inc. Headquarters, Chicago, Illinois, USA) and R version 3.2.3 or later (R Foundation for Statistical Computing, Vienna, Austria).

Primary Outcome	Statistical Test
Children`s Long-Term Survival without Neuro-developmental Disability (3-Years-follow up)	Cochran-Mantel-Haenszel-Test, using 3 strata according to WoG
Secondary Outcome	Statistical Test
Birth before 34 Weeks of Gestation	Cochran-Mantel-Haenszel-Test, Chi-Quadrat Test
Time to Birth	Cox-Regression
Birthweight	van Elteren Test, Wilcoxon-Mann-Whitney Test
Fetal / Neonatal Death	Cochran-Mantel-Haenszel-Test, Chi-Quadrat Test

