Neonatal Morbidity	Cochran-Mantel-Haenszel-Test, Chi-Quadrat Test
Need for Hospitalization (mother)	Cochran-Mantel-Haenszel-Test, Chi-Quadrat Test
Days of Hospitalization (mother)	van Elteren Test, Wilcoxon-Mann-Whitney Test
Maternal Adverse Events	Cochran-Mantel-Haenszel-Test, Chi-Quadrat Test
Pessary Intolerance	Cochran-Mantel-Haenszel-Test, Chi-Quadrat Test
Vaginal Infections	Cochran-Mantel-Haenszel-Test, Chi-Quadrat Test

9.2. Expected number of subjects to be included.

For sample size calculation, we account for the stratified design and assume three equally large gestation groups. For the pessary group, we assume a combined event rate of at least 8% for the primary outcome and for the comparison of the pessary group with the control group we assume an odds ratio of 2.29. This odds ratio correspond to the lower bound of a one-sided confidence interval for the event rate given in van't Hooft (ProTwin Trial¹²). To reach a power of at least 80%, we have to evaluate at least 500 patients, 250 in the pessary group and 250 in the control group. To account for a drop out rate of 25%, overall n=672 pregnant women will be recruited.

9.3. Criteria for termination of the trial.

A non-justified case of maternal death (temporary stop until complete evaluation of the case by an external committee).

9.4. Selection of subjects to be included in each analysis.

The analysis will include all the subjects that have been randomised.

10. Direct Access to Data Source

Direct access will be granted to the authorized monitor, host institution and the regulatory authorities to permit trial-related monitoring, audits and inspections.

11. Quality and Control Assurance

Main investigator and collaborators: In order to ensure the Quality of the data they will provide instructions and training to the sites involved in the trial; review the CRF data; and detail of any other steps taken to ensure quality of research.

The main investigator will sign the study protocol and the “investigator’s commitment; he will apply for the Ethics Committee and the Director’s approval; and he will review the final report of the study.

The collaborators will assess patient’s eligibility, they will inform the patients and ask for the informed consent; and they will be responsible of the CRF and obtaining and registering all data.

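### The birth weight test, which can by itself stop the trial at the interim, is set at newborn level with rank tests and no stated allowance for twin pairs

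*Combined protocol and SAP*

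**What the plan says.** - Section 4.1.2 defines the outcome on children: "Birth weight: median weight (g) of the newborns at birth". A twin pregnancy normally gives two values. The table of tests in section 9.1 assigns birth weight "van Elteren Test, Wilcoxon-Mann-Whitney Test". No pair mean, clustered rank test or mixed model is named.
- The interim paragraph of section 9.1 says: "An interim analysis shall be conducted on key safety parameters after birth of 300 twins". One block of endpoints is placed "on level of the neonates: rate of preterm birth, time to birth, birth weight, death, neonatal morbidity, harm of intervention". Each is tested one-sided at 1%, and the type of test is not named. The consequence is explicit: "The trial will be terminated as negative if a disadvantage for the pessary-treatment can be found in one of these tests".
- The only text on dependence within pairs, also in section 9.1, is: "Events will be analysed for each twin and for single children assuming appropriate random effect regression models".
- Section 4.1.2 defines each preterm birth outcome as a rate of deliveries, yet the interim list places preterm birth and time to birth among the neonate-level items.
- For the primary outcome the unit is settled: section 9.1 defines it as an event in either twin and analyses it by pregnancy.

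**The concern.** Van Elteren and Wilcoxon-Mann-Whitney tests assume that observations within an arm are independent. They are valid for birth weight if each pregnancy contributes one value, and anti-conservative if both newborns enter separately, because twins resemble each other in weight. The plan states a newborn-level outcome, a neonate-level interim and a rank test. Its one provision for pairs is worded for events, which a weight is not.

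At the final analysis the result would be a secondary test with more than 5% false positives. At the interim, one birth weight result against the pessary ends a trial of 672 women before its three-year primary outcome is complete, on a test whose stated 1% level is not met. The same arithmetic is at its worst for preterm birth and time to birth, which the two newborns ordinarily share: counting them per newborn doubles the sample without adding information.

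**Working it through.** **Inputs.** From section 9.1: one-sided 1% at the interim, two-sided 5% at the end, three gestation strata. From section 9.2: equal strata and 672 women recruited, which is 3 strata × 2 arms × 112 pregnancies. The within-pair correlation (ICC) of birth weight is not in the documents; 0.3, 0.5 and 0.7 are assumed.

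**Step 1: the plan's own figures.**
- The stated levels are recovered when twins are uncorrelated. At ICC 0 the simulated van Elteren test on all newborns rejects in 5.0% of runs at the end (two-sided 5%) and 1.0% at the interim (one-sided 1%).
- The sample size is per pregnancy and is not in question. An 8% event rate and an odds ratio of 2.29 give control odds of 2.29 × 0.08/0.92 = 0.199, a rate of 16.6%. A stratified Cochran-Mantel-Haenszel calculation with continuity correction gives 501 women against the stated 500. Dropout gives 500/0.75 = 667 against 672.

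**Step 2: formula.** With *m* pregnancies per arm, two weights each and correlation ICC, the variance of the arm mean is σ²(1 + ICC)/(2*m*). A test that assumes independence uses σ²/(2*m*). Its standardised statistic therefore has standard deviation √(1 + ICC) under no effect, so:
- one-sided 1%: true size = 1 − Φ(2.326/√(1 + ICC))
- two-sided 5%: true size = 2 × [1 − Φ(1.96/√(1 + ICC))]

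**Step 3: results.** The simulations used three equal strata, normal weights, no effect and 20,000 runs.

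| ICC (assumed) | 0.3 | 0.5 | 0.7 |
|---|---|---|---|
| Interim 1%, formula | 2.1% | 2.9% | 3.7% |
| Interim, all newborns, 300 pregnancies | 2.0% | 3.1% | 3.7% |
| Interim, all newborns, 150 pregnancies | 2.1% | 2.9% | 3.7% |
| Interim, pair means, 300 pregnancies | 1.0% | 1.2% | 1.0% |
| Final 5%, formula | 8.6% | 11.0% | 13.3% |
| Final, all newborns, 672 pregnancies | 8.2% | 10.5% | 13.2% |
| Final, pair means, 672 pregnancies | 5.0% | 5.0% | 4.9% |

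The inflation does not depend on the number of pregnancies. The listed test holds its level on one value per pregnancy, including when 5% or 10% of pregnancies give a single weight (0.9% to 1.1% at the interim).

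**Step 4: outcomes shared by the pair.** For preterm birth and time to birth the ICC is close to 1. Counted per newborn, a 1% test has size 1 − Φ(2.326/√2) = 1 − Φ(1.645) = 5.0%.

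**The case against.** **The inflation is conditional.** The plan nowhere says that newborns will be pooled as independent. The definition in section 4.1.2 describes an outcome rather than an analysis unit, and the random-effect sentence shows that the authors had twin correlation in mind. This stands as a limit: the percentages apply only if newborns are pooled, and at an assumed ICC. It does not remove the point, because the stated unit and the stated test, read together, give the wrong size, and nothing in the text directs the analyst elsewhere for birth weight.

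**A reader might infer that every neonate-level interim test lacks a method for pairs.** The documents do not support that. Death, neonatal morbidity and harm are events, and the random-effect sentence in section 9.1 is not limited to the final analysis, so it can cover them. For these it is enough to say that it does.

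**A reader might infer that table and text contradict each other on death and morbidity**, since the table lists "Cochran-Mantel-Haenszel-Test, Chi-Quadrat Test" while the text gives random-effect models. They can be reconciled: a Cochran-Mantel-Haenszel test per pregnancy, as for the primary outcome, and random effects for single children. Naming the unit and the main analysis is a clarification. So is saying whether 300 twins means pregnancies or infants.

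**Multiplicity matters more for false stopping.** With 12 interim tests (six neonatal, six maternal) at 1%, treated as independent for illustration, the chance of some false stop is 1 − 0.99¹² = 11.4%. Inflating birth weight alone at ICC 0.5 gives 1 − 0.99¹¹ × 0.9712 = 13.0%. That is fair as to proportion, but it is no reason to leave a test with the wrong level.

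**The interim looks only for harm**, so some may accept a lenient test there. A known error rate is still needed to interpret a stop.

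**Conclusion.** The point holds for birth weight at both analyses, and for preterm birth and time to birth if they are counted per newborn at the interim. If newborns are pooled, the interim birth weight test runs at about two to nearly four times its stated 1%, and the final test at 8.6% to 13.3% in place of 5%, for ICC 0.3 to 0.7. Two assumptions carry these figures: the ICC, and a literal reading of unit and test. For the interim there is a third, that the rank test in the table is the one used, since the interim paragraph names none.

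A reader might go further and infer that the trial's main conclusion is at risk. It is not. The primary outcome is analysed per pregnancy, the sample size rests on it, and maternal outcomes have one value per woman. Nor can the interim produce a false claim of benefit, because it tests only for disadvantage. The change should be made, but it is a contained correction to one secondary outcome and to the interim.

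**What to change.** In section 9.1:

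1. **Birth weight, final and interim:** apply the listed van Elteren test to one value per pregnancy, the mean of the pair or the single weight where only one is available. Section 5.3 makes the latter relevant: "The death of one twin is not an exclusion criterion for the pessary placement". The median per newborn can remain as a description.
2. **Preterm birth and time to birth, interim:** count once per delivery.
3. **Death, neonatal morbidity and harm, interim:** state that the random-effect models already named for events apply, with pregnancy as the cluster. The size of the random-effect logistic model was not simulated here. A simpler pair-respecting test, a stratified mean-score test on the number of affected twins, stayed at 0.8% to 1.1% for assumed event rates of 5% to 20%.
4. **Clarifications:** name the unit of the Cochran-Mantel-Haenszel test for death and morbidity and which analysis is the main one, and say whether 300 twins means pregnancies or infants.

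**Cost.** The wording is a few sentences. The birth weight comparison becomes average weight per pregnancy rather than per newborn. Infant-level intervals widen by √(1 + ICC) relative to pooling: 14%, 22% and 30% at ICC 0.3, 0.5 and 0.7. Interim power to detect harm falls. For an assumed deficit of 0.3 SD at ICC 0.5 it is about 72% on pair means against 85% pooled with 300 pregnancies, and 39% against 56% with 150. Part of each pooled figure is only its inflated size. The gap between 72% and 39% also shows why the meaning of 300 twins should be stated.

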A medically qualified investigator will assess the relationship of AEs to the study medication.

All SAEs must be reported to the main investigator. He will perform an initial check of the report, request any additional information, and he will notify it to the Ethics Committee. All SAE information will be recorded. It may be appropriate that some SAEs do not require immediate reporting but this must be justified. Justification might be determined, for example, by admission to hospital, or prolongation of hospitalization, where this is to be expected in the underlying disease or condition.

All adverse events (AE) life-threatening or resulting in death will be notified within 24 hours. All AE that are not life-threatening will be notified within 15 days. The rest of AE will be recorded and analyzed at the end of the study.

9. Statistics

9.1. Description of statistical methods.

The primary statistical aim is to compare the primary combined outcome “long-term survival without neuro-developmental disability at 3 years follow up” with a two-sided Cochran-Mantel-Haenszel-Test and a significance level of $\alpha=0.05$. The primary outcome refers to a combined event in any of the twin and will be analysed for all pregnancies with available primary endpoint. The stratified study design is accounted by this stratified test according to the gestation groups.

The main statistical evaluation will be performed at two time points. (1) The complete data set for the secondary endpoints will be available after the last women enrolled in this study has delivered her twins, so the analysis of these outcome parameter will be done right after this event. (2) The primary outcome will be evaluated 3 years after the last woman enrolled in this study has delivered her twins.

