Monitor: he will perform regular monitoring according to ICH GCP. Data will be evaluated for compliance with the protocol and accuracy in relation to source documents. Monitors will verify that the clinical trial is conducted and data are generated, documented and reported in compliance with the protocol, GCP and the applicable and local regulatory requirements.

Serious Breaches: A serious breach is defined as “A breach of GCP or the trial protocol which is likely to effect to a significant degree: (a) the safety or physical or mental integrity of the subjects of the trial; or (b) the scientific value of the trial”. All serious breaches will be notified to the competent Regulatory Authority according to applicable legislation.

12. Ethical issues

The Sponsor, participating Centres and Investigator will ensure that this study is conducted in accordance with the Protocol, the principles of the Declaration of Helsinki (see annex III), ICH Guidelines for Good Clinical Practice and in full conformity with relevant regulations as well as applicable national laws, the German Law and in accordance with regulations and guidelines applicable to clinical trials relating to medical devices.

The protocol, informed consent form, participant information sheet and any applicable documents will be submitted to an appropriate Ethics Committee (EC) and Regulatory Authority for written approval. All substantial amendments to the original approved documents will be also sent to an appropriate Ethics Committee (EC) and Regulatory Authority for written approval. The study will not begin until the approval of the EC and Director's consent.

13. Data Management and Registry File

Patient's participation in the study will be annotated into the medical history.

The main investigator will perform a list with the participant's names, ID numbers and codes. He also will have a file with all the information referring to the study.

All the data will be collected in a database that will be accessed worldwide.

The randomisation will be done on a computer basis. Once entering in the website, if the patient fulfils the inclusion criteria, the computer generated list will randomise the patient to "pessary" or "control" group.

The excluded patients will be also collected in the database.

Every participating centre will have its own randomisation list, and it will be accessible with a username and password.

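### Pessary intolerance is a binding between-arm stopping test, yet controls can have it only after an optional rescue pessary, so the 1% level does not limit how often it ends the trial

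*Combined protocol and SAP*

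**What the plan says.** Section 9.1 plans one interim analysis after the birth of 300 twins. It states that "the following safety endpoints will be assessed by a one-sided test with" a level of 1%. The maternal part of the list ends with "rate of physical or psychological intolerance to pessary, rate of SAR/SAE, death". The consequence is mandatory, and one result is enough: "The trial will be terminated as negative if a disadvantage for the pessary-treatment can be found in one of these tests". The reason given for the 1% level is a comparison with a Bonferroni correction.

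Section 4.1.2 defines intolerance as "discomfort or pain due to the pessary that makes daily life uncomfortable". Under section 5.4, if the cervix shortens later, "pessary treatment may be offered as a rescue treatment up to 32+0 weeks of gestation". This is the only route the documents give by which a control woman could wear the device.

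The table of tests in section 9.1 has a row "Pessary Intolerance" with Cochran-Mantel-Haenszel (CMH) and chi-square tests, both of which compare arms. Section 9.4 includes all randomised subjects, so controls are in the denominator. Nothing exempts this endpoint or makes the rule advisory. Section 9.3 adds only a maternal-death criterion.

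**The concern.** A significance level limits wrong stops only when the null hypothesis can be true. Here the null is equal intolerance in the two arms, but the event needs a pessary. If the device causes any intolerance and not every control receives one, the rates differ because of who was given the device. The comparison can then show that intolerance exists; it cannot show that it is unacceptable. A Bonferroni argument deals with the number of tests and does not address this.

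At stake is the main question. Section 9.1 says "The primary outcome will be evaluated 3 years after the last woman enrolled in this study has delivered her twins". A stop on intolerance would come well before that and label the trial negative, even if every other listed interim test showed no disadvantage.

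**Working it through.** The plan states no operating figure for the interim rule, so there is none to reproduce.

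**Inputs from the documents.** One-sided level 1% and a binding any-one-test rule (9.1); equal allocation (250 and 250 in 9.2).

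**Assumptions.**
- Women per arm, n: 150 if 300 twins means 300 pregnancies, 75 if it means 300 infants.
- True intolerance rate p and share c of controls given a rescue pessary: not in the documents, so varied.
- Rescue recipients have the same intolerance rate p, so the control rate is c × p.
- Interim test: not named, so three standard versions are shown.

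**Step 1: cases that force a stop.** For a pessary-arm and b control cases, with q = (a + b)/(2n):

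- Uncorrected chi-square: z = [(a − b)/n] / √[2q(1 − q)/n]. For 6 v 0 and n = 150: q = 0.02, z = 0.04/0.01617 = 2.47, p = 0.0067. For 5 v 0, p = 0.0121.
- Fisher, b = 0: p = C(n, a)/C(2n, a). For 7 v 0 and n = 150, p = 0.0073. For 6 v 0, p = 0.0148.
- Continuity-corrected: subtract 1/n from the difference. For 8 v 0 and n = 150: z = 0.04667/0.01860 = 2.51, p = 0.0061. For 7 v 0, p = 0.0109.

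Smallest pessary-arm count with p ≤ 0.01, n = 150:

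| Control cases | 0 | 1 | 2 | 3 |
|---|---|---|---|---|
| Uncorrected chi-square | 6 | 8 | 10 | 12 |
| Fisher | 7 | 9 | 11 | 13 |
| Continuity-corrected | 8 | 10 | 12 | 14 |

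At n = 75 the counts against 0, 1 and 2 are the same. CMH with three equal strata agrees at n = 150: over all splits, 6 v 0 gives 0.0060 to 0.0069 uncorrected and 8 v 0 gives 0.0051 to 0.0063 corrected. If all cases fall in one stratum, one case fewer can be enough (5 v 0 at n = 75, uncorrected, p = 0.0098). The counts therefore suffice but are not strict minima.

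**Step 2: how likely no control case is.** P = (1 − c × p)^150. At p = 5% this is 0.995^150 = 47%, 0.99^150 = 22% and 0.98^150 = 5% for c = 10%, 20% and 40%. The zero-control row is not a safe default.

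**Step 3: chance that this test alone stops the trial.** P(stop) is the sum of Bin(a; n, p) × Bin(b; n, c × p) over all (a, b) with p-value ≤ 0.01. By Fisher:

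| n per arm | p | c | P(stop) |
|---|---|---|---|
| 150 | 1% | 0 | 0.1% |
| 150 | 2% | 0 | 3% |
| 150 | 5% | 0 | 63% |
| 150 | 5% | 10% | 43% |
| 150 | 5% | 20% | 29% |
| 150 | 5% | 40% | 12% |
| 150 | 10% | 0 | 99% |
| 75 | 5% | 0 | 8% |
| 75 | 5% | 20% | 4% |

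The choice of test matters too. At n = 150 and p = 5%, uncorrected, Fisher and corrected tests give 77%, 63% and 48% without crossover, and 40%, 29% and 20% with c = 20%.

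As a check, with full crossover (c = 100%) at n = 150 and p = 5% the chance is 0.6% (Fisher) or 1.0% (uncorrected). The nominal level holds when the rates really are equal.

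**Step 4: intolerance rate at which P(stop) reaches 1% and 50% (Fisher).**

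| n per arm | c = 0 | c = 20% | c = 40% |
|---|---|---|---|
| 150 | 1.6% / 4.4% | 1.7% / 7.1% | 2.0% / 14.3% |
| 75 | 3.2% / 8.9% | 3.5% / 14.2% | 4.0% / 26.6% |

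**The case against.** The strongest reply is that this is power, not loss of error control. Any safety test stops more often than its level when real harm exists, and discomfort that disturbs daily life is a real disadvantage. Section 9.1 wants a high level of safety, and whether intolerance alone should end the trial is partly the sponsor's risk-benefit choice. That choice is legitimate, but this test does not express it. Measured against an arm largely without the device, it shows only that some intolerance occurs, and the plan states no level regarded as unacceptable.

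Other points stand in part:

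- **Assumed rates.** The stopping chances rest on assumptions, and women given a rescue pessary later may tolerate it differently. If 300 twins means infants, the chances are much smaller. The defect in the rule does not depend on these rates; its likelihood does.
- **Between-arm reading.** It is inferred for the interim, because the table gives tests for the outcomes generally. It is the natural reading of a disadvantage for the pessary.
- **Follow-up after a stop.** Section 4.9 ends the study after the 3-year follow-up, and nothing says children already enrolled would be dropped. A stop would cost recruitment and power and fix the label, but not necessarily all long-term data.
- **Other endpoints.** Harm of intervention, and the adverse-reaction part of the combined SAR/SAE rate, may share the problem. The first is not defined and the second is mixed with events not attributed to treatment, so the documents do not settle it. This could widen the fix; it does not undermine it.

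**Conclusion.** The concern holds. As written, the rule can end the trial as negative on an excess that follows from who was given the device, and 6 to 8 pessary-arm cases suffice if there is no control case. That is 4.0% to 5.3% of 150 women, or 8.0% to 10.7% of 75. Control cases after rescue raise the count by about two each over the range shown.

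Confidence is high that the rule can stop the trial in this way. How likely it is cannot be determined from the documents: across the assumed rates shown, the chance runs from 0.1% to 99%. Where it stays below 1%, with crossover incomplete, that is because intolerance is rare, not because the 1% level controls it. This should be fixed.

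**What to change.** In section 9.1, take pessary intolerance out of the between-arm tests that trigger automatic termination. Report it at the interim as a rate with an exact 95% confidence interval among women allocated to the pessary: for example 7/150 = 4.7% (1.9% to 9.4%), or 7/75 = 9.3% (3.8% to 18.3%). State who reviews that rate. This denominator includes any woman never fitted and leaves out rescue recipients, which the report should say. Leave the other listed interim tests as they are for this point. The table row for intolerance need not change, since it triggers no stop. Make the change before any interim data are seen.

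The cost is a protocol amendment and no new data. If the amendment is substantial, section 12 applies: "All substantial amendments to the original approved documents will be also sent to an appropriate Ethics Committee (EC) and Regulatory Authority for written approval". The downside is that intolerance would no longer stop the trial automatically. It would have to be judged from the pessary-arm rate by a reviewer whom the sponsor must name.
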